APPENDIX 6. GENETICS

Use/Analysis of DNA

- Inclusion in the HRD-positive malignancies agnostic cohort requires a pre-identified germline and/or somatic pathogenic mutation. Genetic variation may impact a participant's response to study intervention, susceptibility to, and severity and progression of disease.
- DNA samples from blood will be used for confirmation of any pre-identified germline and/or somatic pathogenic mutations. They may also be used to develop tests/assays including diagnostic tests related to lurbinectedin's mechanism of action.
- Additional analyses may be conducted if it is hypothesized that this may help further understand the clinical data.
- The samples may be analyzed as part of a multi-study assessment of genetic factors involved in the response to lurbinectedin or study interventions of this class to understand study disease or related conditions.
- The results of genetic analyses will be reported in a separate study summary.
- The sponsor will store the DNA samples in a secure storage space with adequate measures to protect confidentiality.
- The samples will be retained while research on lurbinectedin continues but no longer than 15 years or other period as per local requirements.

APPENDIX 7. CYP3A INHIBITORS AND INDUCERS**Table 12: Examples of Clinical Inhibitors for P450-mediated Metabolisms (for Concomitant Use Clinical DDI Studies and/or Drug Labeling) (03/06/2020)**

Endpoint	Strongest Inhibitors (≥ 10 -Fold Increase)	Strong Inhibitors (< 10 to ≥ 5 -Fold Increase)	Moderate Inhibitors (≤ 2 to < 5 -Fold Increase)	Weak Inhibitors (≥ 1.25 to < 2 -Fold Increase)
Inhibitors				
CYP3A4	boceprevir, cobicistat ^a , danoprevir and ritonavir ^b , elvitegravir and ritonavir ^b , grapefruit juice ^c , indinavir and ritonavir ^b , itraconazole ^a , ketoconazole, lopinavir and ritonavir ^{a,b} , paritaprevir and ritonavir and (ombitasvir and/or dasabuvir) ^b , posaconazole, ritonavir ^{a,b} , saquinavir and ritonavir ^{a,b} , telaprevir ^a , tipranavir and ritonavir ^{a,b} , telithromycin, troleanandomycin, voriconazole	Clarithromycin ^b , idelalisib, nefazodone, nelfinavir ^a	aprepitant, ciprofloxacin, conivaptan ^d , crizotinib, cyclosporine, diltiazem ^e , dronedarone ^a , erythromycin, fluconazole, fluvoxamine, imatinib, tofisopam, verapamil ^a	chlorzoxazone, cilostazol, cimetidine, clotrimazole, fosaprepitant, istradefylline, ivacaftor ^a , lomitapide, ranitidine, ranolazine ^a , ticagrelor ^a
Inducers				
Endpoint	Strong Inducers ($\geq 80\%$)		Moderate Inducers ($\geq 50\%$ to $< 80\%$)	Weak Inducers ($\geq 20\%$ to $< 50\%$)

CYP3A	apalutamide, carbamazepine, enzalutamide, mitotane, phenytoin, rifampin, St. John's wort ^f	bosentan, efavirenz, etravirine, phenobarbital, primidone	armodafinil, modafinil ^g , rufinamide
-------	---	---	--

Abbreviations: AUC = area under the concentration-time curve.

This table is prepared to provide examples of clinical inhibitors and inducers and is not intended to be an exhaustive list. DDI data were collected based on a search of the University of Washington Metabolism and Transport Drug Interaction Database [Hachad et al. (2010), Hum Genomics, 5(1):61].

- ^a Inhibitor of P-gp (defined as those increasing AUC of digoxin to ≥ 1.25 -fold).
 - ^b Ritonavir is usually given in combination with other anti-HIV or anti-HCV drugs in clinical practice. Caution should be used when extrapolating the observed effect of ritonavir alone to the effect of combination regimens on CYP3A activities.
 - ^c The effect of grapefruit juice varies widely among brands and is concentration-, dose-, and preparation-dependent. Studies have shown that it can be classified as a “strong CYP3A inhibitor” when a certain preparation was used (eg, high dose, double strength) or as a “moderate CYP3A inhibitor” when another preparation was used (eg, low dose, single strength).
 - ^d The classification is based on studies conducted with intravenously administered conivaptan.
 - ^e Diltiazem increased AUC of certain sensitive CYP3A substrates (eg, buspirone) more than 5-fold.
 - ^f The effect of St. John's wort varies widely and is preparation-dependent.
 - ^g Based on effect of 200 mg/day modafinil. A higher dose (400 mg/day) modafinil had larger induction effect on CYP3A.
- Source: FDA Drug Development and Drug Interactions: Table of Substrates Inhibitors and Inducers 2020

APPENDIX 8. TUMOR ASSESSMENTS GUIDELINES

The full RECIST version 1.1 guideline is contained in the following:

Tumor assessments will include all known or suspected disease sites. Imaging may include chest, abdomen, and pelvis CT or MRI scans. Bone scans or 18-Fluorodeoxyglucose Positron Emission Tomography (18FDG-PET) and brain CT or MRI scans are also required at baseline (28-day screening period) if brain metastasis is suspected or if participants have symptoms of brain metastasis except in patients with lung cancer. All patients with lung cancer will require brain scan.

Bone lesion(s) identified at baseline by bone scan will be further assessed by CT or MRI as per local practice (where bone scans are not used as a routine restaging tool) and subsequently re-assessed by CT or MRI as per the tumor assessment schedule as an alternative to bone scans. Bone scans will only be repeated during study as clinically indicated (eg, participant describes new or worsening bone pain, or has increasing alkaline phosphatase level, or other signs and symptoms of new/progressing bone metastases), at the time of CR confirmation, and at every other tumor assessment visit (every 12 weeks) if considered local standard of care.

MRI brain scans must be included in subsequent tumor assessments if a participant has brain metastases at baseline; otherwise, brain will be evaluated only when clinically indicated.

CR and PR must be confirmed with repeat imaging performed at least 4 weeks after initial documentation of response. For equivocal findings of progression (eg, very small and uncertain new lesions; cystic changes or necrosis in existing lesions), treatment may continue until the next scheduled assessment. If at the next scheduled assessment, progression is confirmed, the date of progression should be the earlier date when progression was suspected. In the absence of clinical deterioration, participants with PD can remain on the current study treatment until PD is confirmed by subsequent scan at PI's discretion.

Baseline and all scans performed for treatment evaluation will be collected and stored for future evaluation if a cohort or cohorts for further expansion and/or regulatory submission. Measurable or evaluable lesions that have been previously irradiated will not be considered target lesions unless an increase in size has been observed following completion of radiation therapy.

The same radiographic procedure used to assess disease sites at screening should be used throughout the study (eg, the same contrast protocol for CT scans). Response will be assessed by the investigator using RECIST v1.1 criteria. The same evaluator, if possible, should perform assessments to ensure internal consistency across visits. Results must be reviewed by the investigator before dosing at the next cycle.

Additional radiological tumor assessments should also be conducted whenever disease progression is suspected (eg, symptomatic deterioration).

Jazz Pharmaceuticals
JZP712

Protocol JZP712-201-02
Amendment 02

If a participant starts a new anticancer therapy before documented disease progression, then tumor assessments should be continued per the SoA (if feasible) until documentation of disease progression or death, whichever occurs first.

APPENDIX 9. PROTOCOL AMENDMENT HISTORY

The Protocol Amendment Summary of Changes Table for the current amendment is located directly before the Table of Contents (TOC).

Amendment 01: 12 August 2021

This amendment was considered to be substantial based on the criteria set forth in Article 10(a) of Directive 2001/20/EC of the European Parliament and the Council of the European Union.

Overall Rationale for the Amendment

The overall rationale for the changes in this protocol amendment was to include Agency-requested feedback. Following is a list of important changes in Amendment 01; editorial changes are not included in this list.

Section # and Name	Description of Change	Brief Rationale
5.1/Inclusion Criteria, Disease Characteristics for Each Cohort; Criterion 9a; Criterion 10a	Added “advanced (metastatic and/or unresectable)”	To provide additional clarity that participants in all cohorts must have advanced disease
5.1/Inclusion Criterion 11a	Changed “...pancreas or gastric/esophageal solid tumors” to “...pancreas, gastric, or esophageal solid tumors”	To provide additional clarity
5.1/Inclusion Criterion 11b	Changed “no more than 3 prior lines of systemic therapies” to “no more than 3 prior lines of chemotherapy” and updated the supporting text for this criterion	To allow hormone therapies, targeted therapies, and/or other biological agents
6.7/Study Intervention Dose Delay and Reduction Rules	Deleted “and any grade febrile neutropenia” as a reason participants may continue with secondary G-CSF prophylaxis instead of dose reduction	For alignment with the approved Lurbinctedin USPI

Jazz Pharmaceuticals
JZP712

Protocol JZP712-201-02
Amendment 02

DocuSigned by:

 Signer Name: 
Signing Reason: I approve this GxP document
Signing Time: Oct-06-2022 | 2:23 PM PDT
FFD8BEEF5ED343EC87073204CFB038A6

## 1. LIST OF ABBREVIATIONS

**Table 1: List of Abbreviations**

Abbreviation	Term
AE	Adverse Event
AAGP	Alpha-1 Acid Glycoprotein
ALT	Alanine Aminotransferase
AP	Alkaline Phosphatase
AST	Aspartate Aminotransferase
ATC	Anatomical Therapeutic Chemical
BOR	Best Overall Response
BLLQ	Below the Lower Limit of Quantification
BPP	Bayesian Posterior Probability
BSA	Body Surface Area
CI	Confidence Interval
CR	Complete Response
CrCl	Creatinine Clearance
CPK	creatinine phosphokinase
CRF	Case Report Form
CSR	Clinical Study Report
CTCAE	Common Terminology Criteria for Adverse Events
CV	coefficient of variation
DCR	Disease Control Rate
DOR	Duration of Response
ECG	Electrocardiogram
ECHO	Echocardiogram
ECOG	Eastern Cooperative Oncology Group
EOS	end-of-study
EOT	end of treatment
eCRF	electronic case report form
GGT	Gamma-glutamyl transferase
HBCAb	hepatitis B core antibody
HBsAg	hepatitis B surface antigen

## Jazz Pharmaceuticals, Inc.

JZP712-201 Statistical Analysis Plan - Protocol Amendment

2

HER-2	Human Epidermal Growth Factor receptor 2
HIV	human immunodeficiency virus
HRD	homologous recombination deficient
ICF	Informed Consent Form
ICH	International Conference on Harmonization
IRT	Interactive Response Technology
K-M	Kaplan-Meier
PD-NEC	poorly differentiated neuroendocrine carcinoma
LDH	lactate dehydrogenase
LLOQ	Lower Limit of Quantification
MedDRA	Medical Dictionary for Regulatory Activities
NCI	National Cancer Institute
ORR	Overall Response Rate
OS	Overall Survival
PD	Progressive Disease
PFS	Progression-free Survival
PR	Partial Response
PT	Preferred Term
PTT	partial thromboplastin time
RECIST	Response Evaluation Criteria in Solid Tumors
Q3W	every 3 weeks
SAE	Serious Adverse Event
SAP	Statistical Analysis Plan
SAS	Statistical Analysis Software
SD	Stable Disease
SOC	System Organ Class
SD	Standard Deviation
TEAE	Treatment Emergent Adverse Event
TPP	Time to Progression
TTR	Time to Response
UC	urothelial cancer

Jazz Pharmaceuticals, Inc.

JZP712-201 Statistical Analysis Plan - Protocol Amendment

2

ULN	Upper Limit of Normal
UTD	Unable to determine
WHO	World Health Organization

Jazz Pharmaceuticals, Inc.

JZP712-201 Statistical Analysis Plan - Protocol Amendment

2

## **2. MODIFICATION HISTORY**

Version History for SAP:

Version	Date	Description
Original		

Jazz Pharmaceuticals, Inc.

JZP712-201 Statistical Analysis Plan - Protocol Amendment

2

### **3. INTRODUCTION**

The purpose of this statistical analysis plan (SAP) is to describe in detail the statistical methodology and planned analyses to be conducted for Study *JZP712-201* for inclusion in the clinical study report (CSR). The current version of the SAP is based on Protocol Amendment 2 dated 14-Oct-2022. Any additional analyses or deviation from the analyses outlined in this plan will be documented with rationale in the final CSR. Mock tables, listings, and figure shells will be provided in a separate supporting document.

This SAP complies with the International Conference on Harmonization (ICH) Harmonized Tripartite Guideline Topic E9, Statistical Principles for Clinical Trials.

All decisions regarding the final analysis of the study results, as defined in this SAP, have been made prior to database lock of the study data.

## **4. STUDY OBJECTIVES AND ENDPOINTS**

### **4.1. Study Objectives**

#### **4.1.1. Primary Objective**

- To evaluate the antitumor activity of lorbinecetin in the selected advanced solid tumors.

#### **4.1.2. Secondary Objectives**

- To evaluate the overall safety profile of lorbinecetin in the selected advanced solid tumors.
- To assess other antitumor efficacy parameters of lorbinecetin in the selected advanced solid tumors.

- [REDACTED]
- [REDACTED]

### **4.2. Study Endpoints**

#### **4.2.1. Primary Endpoint**

- Investigator-assessed objective response rate (ORR) according to RECIST v1.1.

#### **4.2.2. Secondary Endpoints**

- Adverse events (AEs) and serious adverse events (SAEs) as graded by NCI CTCAE v.5.0.
- Investigator-assessed duration of response (DOR) according to RECIST v1.1.

Jazz Pharmaceuticals, Inc.

JZP712-201 Statistical Analysis Plan - Protocol Amendment

2

- [REDACTED]
- [REDACTED]

## 5. STUDY DESIGN

### 5.1. Summary of Study Design

This is an open-label, multicenter, phase 2 study of lorbrena (lurbinectedin) monotherapy in participants with advanced (metastatic and/or unresectable) solid tumors.

The study population comprises participants in 3 cohorts with advanced (metastatic and/or unresectable) urothelial cancer (UC), advanced (metastatic and/or unresectable) poorly differentiated neuroendocrine carcinoma (PD-NEC), or homologous recombination deficient (HRD)-positive tumor agnostic malignancies.

This is a signal-seeking study of lorbrena 3.2 mg/m^2 monotherapy Q3W. Review of the safety and efficacy data will be performed on an ongoing basis by the sponsor. The sponsor may decide to close a cohort or cohorts due to safety concerns, lack of efficacy or any other reasons. A cohort or cohorts may be expanded at the sponsor's discretion to greater than 20 participants if an efficacy signal is observed without any safety concerns.

Beginning on Cycle 1 Day 1, participants still on study treatment will undergo tumor assessments per RECIST v1.1 every 6 weeks ( $\pm$  7 days) through Week 36, regardless of treatment dose delays. After Week 36, tumor assessments will be required every 12 weeks ( $\pm$  14 days). Participants will undergo tumor assessments until radiographic disease progression, withdrawal of consent, lost to follow-up, study termination by the sponsor, or death, EOT visit, or study termination, whichever occurs first. After the EOT visit, all participants will be followed for survival by a telephone call every 3 months until at least 80% of participants in each cohort have died or withdraw consent or are lost to follow-up. If a cohort closes due to futility, the OS follow-up for that cohort will end.

[figure not shown]
The projected study duration for each participant will be approximately 17 months including: Screening Period (28 days), Intervention Period (9 months), Safety Follow-up Period (30 days), and OS Follow-up Period (6 months).

An overview of the study design is illustrated in [Figure 1](#) and details regarding study assessments are in [Appendix 1](#).

Jazz Pharmaceuticals, Inc.

JZP712-201 Statistical Analysis Plan - Protocol Amendment

2

**Figure 1: Study Schematic**

Abbreviations: C = cycle; D = day; E/D = early discontinuation; EOS = end of study; HRD = homologous recombination deficient; OS = overall survival; Q3W= every 3 weeks; wks = weeks.

## 5.2. Study Treatment

Participants will receive lubrinectedin 3.2 mg/m^2 IV on Day 1 of Q3W cycle. Lubrinectedin (JZP712) also known as PM01183 is a lyophilized powder for concentrate for solution for infusion. All participants will receive standard antiemetic prophylaxis before each treatment infusion.

For any treatment delay due to treatment-related AEs lasting more than 1 week, a dose reduction should be implemented upon recovery. Participants may continue the study treatment at a reduced dose if they present any of the following:

- Grade  $\geq 3$  treatment-related nonhematological toxicity. Exceptions are Grade  $\geq 3$  nausea and/or vomiting not optimally treated, Grade 3 asthenia lasting  $\leq 3$  days, Grade 3 diarrhea lasting  $\leq 2$  days or not optimally treated, Grade 3 transient ALT/AST elevations that are rapidly reversible and not leading to subsequent delays, and nonclinically relevant biochemical abnormalities
- Grade 4 thrombocytopenia or Grade 3 thrombocytopenia concomitantly with Grade  $\geq 3$  bleeding
- Grade 4 neutropenia, any grade febrile neutropenia or neutropenia associated with infection/sepsis
  - Note: Participants with Grade 4 neutropenia may continue with secondary G-CSF prophylaxis instead of dose reduction. However, if the episode is repeated despite secondary G-CSF prophylaxis, then the dose must be reduced.
- Frequent or prolonged ( $> 1$  week) dose delays due to treatment-related AEs
- Unacceptable toxicity in the judgement of the investigator.

Participants who experience Grade 3/4 hypersensitivity reactions will be discontinued from study intervention.

Jazz Pharmaceuticals, Inc.

JZP712-201 Statistical Analysis Plan - Protocol Amendment

2

Dose reduction levels are shown in Table 2. Up to 2 dose reductions are allowed per participant.

**Table 2: Lurbinectedin Dose Reduction Levels**

Dose Reduction	Lurbinectedin Dose (mg/m  )
1 (starting dose)	3.2
-1	2.6
-2	2.0

Participants who continue to experience treatment-related toxicity and/or frequent dose delays after permitted dose reductions should be discontinued from the study. However, they can continue receiving the study intervention if objective clinical benefit is adequately documented by the Investigator, and upon agreement with the Sponsor. Once the dose has been reduced for an individual participant, it will not be re-escalated under any circumstance.

Study intervention will continue until confirmed disease progression, withdrawal of participant consent, participant lost to follow-up, unacceptable toxicity, or the study or individual cohort is terminated by the sponsor, whichever comes first.

### 5.3. Power and Sample Size Considerations

This is a nonrandomized multi-cohort signal finding study designed to assess the antitumor activity of lurbinectedin in terms of the ORR according to the RECIST v1.1 in three different advanced (metastatic and/or unresectable) solid tumors cohorts.

This study includes up to a total of 60 participants in the initial assessment of efficacy in which each tumor cohort includes up to 20 participants. If there is evidence of efficacy in a cohort, enrollment beyond 20 participants in the individual cohort may be considered.

Each cohort will have up to 4 stages of enrollment: stage 1 at n = 12 and stage 2 at n = 20 for futility testing; if a cohort is expanded beyond 20 participants, the study may enroll into stage 3 with an interim analysis to assess efficacy at n = 35, and a final stage 4 at n = 100 for the final analysis.

If there are  $\geq 4$  responses (a target of 20% ORR) out of 20 participants in a cohort, the lower bound of 70% confidence interval (CI) of ORR (10.5% to 33.4%) will exclude a 10% ORR (Table 3) and the cohort may continue. This will provide approximately 85% confidence that the true ORR is  $> 10\%$ , where a 10% or lower response rate is not clinically meaningful.

**Table 3: Two-sided, Exact CI of ORR Under Varying Scenarios for n = 20**

Sample Size	No of Responders	Observed ORR (%)	70% CI of ORR (%)	80% CI of ORR (%)	90% CI of ORR (%)	95% CI of ORR (%)
20	4	20	(10.5, 33.4)	(9.0, 36.1)	(7.1, 40.1)	(5.7, 43.7)
	5	25	(14.4, 38.8)	(12.7, 41.5)	(10.4, 45.6)	(8.7, 49.1)
	6	30	(18.5, 44.0)	(16.6, 46.7)	(14.0, 50.8)	(11.9, 54.3)
	7	35	(22.8, 49.1)	(20.7, 51.8)	(17.7, 55.8)	(15.4, 59.2)
	8	40	(27.2, 54.1)	(24.9, 56.7)	(21.7, 60.6)	(19.1, 63.9)

Abbreviations: ORR: Objective response rate; CI: Confidence interval.

Jazz Pharmaceuticals, Inc.

JZP712-201 Statistical Analysis Plan - Protocol Amendment

2

If there are  $\geq 8$  responses (22.9% ORR) out of 35 participants in a cohort, the lower bound of 95% CI of ORR (10.4% to 40.1%) will exclude a 10% ORR (Table 4) and the cohort may continue enrollment up to a total of 100 participants.

If there are  $\geq 20$  responses (20% ORR) out of 100 participants in a cohort, the lower bound of 95% CI of ORR (12.7% to 29.2%) will exclude a 10% ORR (Table 4).

**Table 4: Two-sided, Exact CI of ORR Under Varying Scenarios for n = 35 and n=100**

Sample Size	No of Responders	Observed ORR (%)	95% CI of ORR (%)
35	7	20.0	(8.4, 36.9)
	8	22.9	(10.4, 40.1)
	9	25.7	(12.5, 43.3)
100	18	18.0	(11.0, 26.9)
	19	19.0	(11.8, 28.1)
	20	20.0	(12.7, 29.2)

Abbreviations: ORR: Objective response rate; CI: Confidence interval.

#### 5.4. Randomization and Blinding

Not applicable. This is a nonrandomized multi-cohort, open-label signal finding study.

#### 5.5. Interim Analysis

Review of the safety and efficacy data will be performed by the sponsor on an ongoing basis in this study.

Assessment of the observed responses will be performed after enrollment of approximately 12 and 20 efficacy-evaluable participants for treatment benefit. If no confirmed response per RECIST v1.1 is observed in approximately the first 12 evaluable participants of a cohort with at least two post-baseline evaluable tumor assessments, the recruitment of participants in that cohort will be stopped. If there are  $\leq 3$  confirmed responses in the first 20 evaluable participants of a cohort, the recruitment of participants in the cohort will be stopped. There will be no pause in enrollment during the interim analysis of the first 12 evaluable participants of a cohort, and the futility boundary will be adjusted based on the actual number of participants at each stage.

Interim futility monitoring will be implemented through the Bayesian Posterior Probability (BPP) approach with the prior distribution for ORR assumed to be Beta (0.5, 0.5). [Table 5](#) has the operating characteristics for futility of stopping at 12 and 20 participants.

If no response is observed in the first 12 participants of a cohort, there is an 89% posterior probability that the actual response rate is no more than 10%. If there are  $\leq 3$  responses in the first 20 participants of a cohort, there is a 70% posterior probability that the actual response rate is no more than 20%.

Jazz Pharmaceuticals, Inc.

JZP712-201 Statistical Analysis Plan - Protocol Amendment

2

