9.3. Analysis Sets

Participant Analysis Set	Description
Enrolled	All participants who sign the informed consent form
Safety	All participants who take at least 1 dose of study treatment. This is the primary set for safety analyses
Efficacy-evaluable	Participants in the Safety analysis set with measurable disease at baseline and one of the following: (a) at least 1 post-baseline evaluable tumor assessment, (b) clinical progression, or (c) death
[REDACTED]	[REDACTED]
[REDACTED]	[REDACTED]

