9.5. Interim Analysis

Review of the safety and efficacy data will be performed by the sponsor on an ongoing basis in this study. Assessment of the observed responses will be performed after enrollment of approximately 12 and 20 efficacy-evaluable participants for treatment benefit. If no confirmed response per RECIST v1.1 is observed in approximately the first 12 evaluable participants of a cohort, the recruitment of participants in that cohort will be stopped. If there are ≤ 3 confirmed responses in the first 20 evaluable participants of a cohort, the recruitment of participants in the cohort will be stopped. There will be no pause in enrollment during the interim analysis of the first 12 evaluable participants of a cohort, and the futility boundary will be adjusted based on the actual number of participants at each stage.

Interim futility monitoring will be implemented through the BPP approach with the prior distribution for ORR assumed to be Beta (0.5, 0.5). Table 10 has the operating characteristics for futility of stopping at 12 and 20 participants. If no response is observed in the first 12 participants of a cohort, there is an 89% posterior probability that the actual response rate is

no more than 10%. If there are ≤ 3 responses in the first 20 participants of a cohort, there is a 70% posterior probability that the actual response rate is no more than 20%.

Table 10: Posterior Probability for Interim Futility Monitoring

No Participants	Futility Stopping	Prob ($\theta \leq 10\% r, n$)	Prob ($\theta \leq 15\% r, n$)	Prob ($\theta \leq 20\% r, n$)
12	0	89%	95%	98%
20	1	76%	91%	97%
20	2	46%	72%	87%
20	3	21%	47%	70%

θ = True response rate; r = the observed responses; n = the number of participants

The SAP will describe the planned interim analyses in greater detail.

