**Table 5: Posterior Probability for Interim Futility Monitoring**

No Participants	Futility Stopping	Prob ( $\theta \leq 10\%   r, n$ )	Prob ( $\theta \leq 15\%   r, n$ )	Prob ( $\theta \leq 20\%   r, n$ )
12	0	89%	95%	98%
20	1	76%	91%	97%
20	2	46%	72%	87%
20	3	21%	47%	70%

$\theta$  = True response rate;  $r$  = the observed responses;  $n$  = the number of participants

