## 6. ANALYSIS SETS

For purposes of analysis, the following populations are defined:

Analysis Set	Description
Enrolled	All participants who sign the informed consent form (ICF).
Safety	All participants who took at least one dose of study treatment. This is the primary set for safety analyses.
Efficacy evaluable	Participants in Safety analysis set with measurable disease at baseline and one of the following: (a) at least one post-baseline evaluable tumor assessment, (b) clinical progressions, or (c) death.
[REDACTED]	[REDACTED]
[REDACTED]	[REDACTED]

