#### **7.8. Changes to Planned Analyses**

None.

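### SAP 5.5 restricts the stage-1 futility count to participants with two post-baseline scans, which Protocol 9.5 does not; read as written, the early stop is weaker and later, while total stopping by n = 20 barely changes

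*SAP*

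**What the plan says.** Protocol 9.5 closes a cohort to recruitment when no confirmed response is seen in "approximately the first 12 evaluable participants of a cohort, the recruitment of participants in that cohort will be stopped". It sets no minimum number of scans or length of follow-up, and adds: "The SAP will describe the planned interim analyses in greater detail".

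SAP 5.5 repeats the rule but applies it to "approximately the first 12 evaluable participants of a cohort with at least two post-baseline evaluable tumor assessments". The extra condition appears nowhere else:

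- The efficacy-evaluable set needs only "at least 1 post-baseline evaluable tumor assessment, (b) clinical progression, or (c) death" (Protocol 9.3), or "at least one post-baseline evaluable tumor assessment, (b) clinical progressions, or (c) death" (SAP 6).
- The SAP's stage-2 rule stops on three or fewer "confirmed responses in the first 20 evaluable participants of a cohort, the recruitment of participants in the cohort will be stopped", with no scan condition.
- SAP Table 5 ("Posterior Probability for Interim Futility Monitoring") is indexed only by responses and number of participants.
- SAP 7.8 ("Changes to Planned Analyses") reads: None.

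Protocol Appendix 8 requires a response to be confirmed by repeat imaging at least 4 weeks later.

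**The concern.** The added words decide who enters the denominator of 12, not when the look takes place. An evaluable participant who dies, progresses clinically, or has progression at the first scan with no rescan never reaches two post-baseline assessments and so is never counted. Because confirmation needs a second scan, everyone permanently left out is a non-responder. A participant whose response is first seen at scan 1 is held back only until the next scan.

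Zero responses among 12 counted participants therefore means zero among 12 or more evaluable ones. With mature data and the same ordering, a stop under the SAP implies a stop under the protocol, but not the reverse. The two documents can then give different recruitment decisions at stage 1 on the same data. What is at stake is the purpose of the first look, which is to close an inactive cohort before it reaches 20.

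**Working it through.** **Inputs.** Stage 1: stop on 0 of 12. Stage 2: stop on 3 or fewer of 20. Prior Beta(0.5, 0.5). A response rate of 10% or lower is not clinically meaningful (Protocol 9.2, SAP 5.3); the desired rate is 20% or more (Protocol 4.2). Let p be the true confirmed response rate and f the share of evaluable participants who never have a second post-baseline scan. The documents do not give f; I assume 0.1, 0.2 and 0.3.

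**The plan's own figure.** For 0 of 12 the posterior is Beta(0.5, 12.5), and P(ORR ≤ 10%) = 0.892. The stated 89% is right, and the other rows of the table also reproduce.

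**Protocol wording.** P(stage-1 stop) = (1 − p)^12: 0.540 at p = 0.05, 0.282 at p = 0.10, 0.069 at p = 0.20.

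**SAP wording read as a filter.** Only non-responders are removed, so the response rate among those counted is p/(1 − f) and P(0 of 12 counted) = (1 − p/(1 − f))^12. Filling 12 places takes 12/(1 − f) evaluable participants on average: 13.3, 15.0 and 17.1. If the places are not filled before the 20th evaluable participant, stage 1 merges with the n = 20 look. The chance that they are filled in time is P(Bin(19, 1 − f) ≥ 12) = 0.9997, 0.977 and 0.818. Hence

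P(stage-1 stop before the 20th) = (1 − p/(1 − f))^12 × P(Bin(19, 1 − f) ≥ 12).

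Example, p = 0.10 and f = 0.3: (1 − 0.1429)^12 × 0.818 = 0.157 × 0.818 = 0.129.

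| True ORR | Protocol | f = 0.1 | f = 0.2 | f = 0.3 |
|---|---|---|---|---|
| 5% | 54.0% | 50.4% | 45.0% | 33.6% |
| 10% | 28.2% | 24.3% | 19.7% | 12.9% |
| 20% | 6.9% | 4.9% | 3.1% | 1.4% |

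**Disagreement at stage 1** (protocol stops, SAP does not) is the protocol column minus the SAP column:

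| True ORR | f = 0.1 | f = 0.2 | f = 0.3 |
|---|---|---|---|
| 5% | 4% | 9% | 20% |
| 10% | 4% | 9% | 15% |
| 20% | 2% | 4% | 5% |

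**Total stopping by n = 20.** Under the protocol this is P(X20 ≤ 3) + (1 − p)^12 × P(Bin(8, p) ≥ 4):

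- p = 0.05: 0.9841 + 0.5404 × 0.0004 = 0.9843
- p = 0.10: 0.8670 + 0.2824 × 0.0050 = 0.8685
- p = 0.20: 0.4114 + 0.0687 × 0.0563 = 0.4153

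The first term is the n = 20 rule alone. The filter can at most remove the second term, which is 0.4 percentage points at p = 0.20 and about 0.1 at p = 0.10.

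**The case against.** The strongest reply is that this is permitted detail. Protocol 9.5 leaves interim specifics to the SAP, says approximately 12, and fixes no follow-up. Since a confirmed response cannot exist before a second scan, two scans is a natural readiness condition; on that reading the probabilities equal the protocol's, and None in SAP 7.8 is defensible. The condition also meets a real weakness. If 1, 2 or 3 of the 12 have had only one scan, a literal reading of Protocol 9.5 could stop up to 0.8^11 = 8.6%, 0.8^10 = 10.7% or 0.8^9 = 13.4% of cohorts at the 20% target, against 6.9% with mature data. The aim therefore stands. But the words attach to the participants counted, and nothing says that early failures stay in.

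The adjustment of the boundary to the actual number of participants does not close the gap, because no posterior cut-off is given. If the 89% at 0 of 12 were the cut-off (an assumption), one response would not qualify even at 20, where Table 5 gives 76%.

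The size is also open to challenge. f is assumed, and several provisions lower it: treatment to confirmed progression (Protocol 4.1, 7.1), rescanning after progression and extra scans when progression is suspected (Appendix 8), and the EOT scan (7.1). Participants saved cannot be read off the tables, because enrollment does not pause. If 8 more enroll in the 12 weeks after the 12th (an illustrative rate), 20 are already in before a two-scan look. Both points limit the size, not the direction.

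**Conclusion.** The wording difference is real and its direction is certain once the phrase is read as a filter: the stage-1 stop is stricter than the protocol's and no earlier. The size is less certain. It rests on that reading, on an assumed f of 0.1 to 0.3, and on mature data taken in the same order. I rate the point minor, with high confidence in the difference and its direction and moderate confidence in its size.

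A reader might infer more than the documents support:

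- That the SAP changes which cohorts go forward. It does not in any material way: total stopping by n = 20 stays at about 98%, 87% and 41–42% at true rates of 5%, 10% and 20%. The consequence is a weaker, later early stop in inactive cohorts.
- That the 89% is wrong. It is correct for 0 of 12.
- That every disagreement is an SAP error. Disagreement arises when a confirmed response appears after the 12th evaluable participant, or when the 12 places are not filled before the n = 20 look. In the first case continuing can be reasonable: 1 of 15 gives a posterior of only 62% that ORR is at most 10%.

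**What to change.** Change SAP 5.5 only, replacing the restriction with a maturity condition, for example:

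> The first 12 efficacy-evaluable participants, assessed once each has had at least two post-baseline tumor assessments or has had PD, clinical progression, death, new anticancer therapy or study discontinuation before the second (counted as non-responders); a response awaiting confirmation is followed to its confirmatory scan before the rule is applied.

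If the restriction is intended, declare it in SAP 7.8 with its effect on the stage-1 stop.

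The cost is one sentence, with no protocol amendment, extra participants or procedures. There are two downsides. The look may wait for a second or confirmatory scan (scans are 6 weeks apart through Week 36) while enrollment continues. Stage-1 stopping at the 20% target would be about 7%, rather than about 1–5% under the filter for the assumed f, with total stopping essentially unchanged.
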